3.4. Exploratory Objective

To explore Quality of Life in subjects with POAG or OHT (using the Glaucoma Quality of Life (GQL)-15 Questionnaire) when given DE-126 or Timolol for 3 months.

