ⁿ Blood sampling for the PGx laboratory research study may be performed at any visit after PGx informed consent obtained, subject randomized, and study drug dosing has begun. The earliest this sample is to be collected at Visit 3 (Week 2) but it may also be collected at any later time during the study after Visit 2 (Eligibility/Baseline) or at a separate post-study visit, if necessary.

^o At Visit 3, 4, and 5, subject will be reminded to take evening dose on the day before each visit. At Follow-up Period, subject will be contacted by a phone call to confirm AE after 2 weeks post last study drug administration.

^p GQL-15 questionnaire will be administered by subject.

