8.1.3. Visit 2 (Baseline, Day 1)

- Update concomitant medications and procedures/therapies.
- Confirm the subject has complied with the required wait/washout period for ocular hypotensive medication(s), or contact lenses use, if required.
- Query the subject regarding AEs.
- As per Schedule of Events and Procedures ([Table 3](#)), perform the following procedures or assessments immediately before the 08:00 (± 60 min) IOP measurement (all ophthalmic procedures to be performed in both eyes):
 - BCVA (before the 08:00 (± 60 min) IOP measurement).
 - If more than 10 letters in BCVA were lost compared to the screening visit, then refraction should be performed again.
 - Slit-lamp biomicroscopy (before the 08:00 (± 60 min) IOP measurement).
 - Perform vital signs (blood pressure/pulse rate) measurements (before the 08:00 (± 60 min) IOP measurement).
 - Obtain urine and perform a urine pregnancy test, if the subject is a female of childbearing potential (before the 08:00 (± 60 min) IOP measurement).
- Perform IOP measurement at 08:00 (± 60 min).
- If subject meets the 08:00 IOP eligibility requirements, schedule additional IOP measurements at 10:00.
- Perform IOP measurement at 10:00 (± 60 min).
- If subject meets the 08:00 and 10:00 IOP eligibility requirements, schedule additional IOP measurements at 16:00.

- Perform GQL-15 questionnaire at any time during this visit prior to 16:00 IOP measurement.
- Perform IOP measurement at 16:00 (± 60 min).
- Perform pupil dilation in both eyes after the 16:00 (± 60 min) IOP measurement.
- Perform ophthalmoscopy with pupil dilation in both eyes immediately after the 16:00 (± 60 min) IOP measurement.
- Perform final review of eligibility criteria after the 16:00 (± 60 min) IOP measurement. The subject will then be randomized, via Medidata Rave RTSM.
- A subject who does not meet eligibility criteria or will not otherwise continue in the study is considered a screen failure.
- After the subject has been randomized to a treatment arm, and assigned a treatment kit by Medidata Rave RTSM, an authorized unmasked study staff member, other than the Investigator or Examiner, must:
 - Dispense the assigned kit to the subject which will contain the following:
 - Two bottles of study drug labeled “morning” and
 - Two bottles of study drug labeled “evening”
 - OR
 - Two bottles of study drug labeled morning/evening.

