8.1.6. Visit 5 (Month 3, Day 90 ±7) / Study Exit/ Early Termination

- Update concomitant medications and procedures/therapies.
- An authorized unmasked study staff member, other than the Investigator or Examiner should query the subject regarding dosing compliance and check the subject paper diary of daily medication recording.
- Query the subject regarding AEs.
- As per Schedule of Events and Procedures ([Table 3](#)), perform the following procedures or assessments immediately before the 08:00 (±60 min) IOP measurement (all ophthalmic procedures to be performed in both eyes):
 - BCVA (before the 08:00 (±60 min) IOP measurement)
 - If more than 10 letters in BCVA were lost compared to the screening visit, then refraction should be performed again.
 - Slit-lamp biomicroscopy (before the 08:00 (±60 min) IOP measurement)
 - Perform vital signs (blood pressure/pulse rate) measurements (before the 08:00 (±60 min) IOP measurement).
 - Obtain urine and perform a urine pregnancy test, if the subject is a female of childbearing potential (before the 08:00 (±60 min) IOP measurement).
- Perform IOP measurement at 08:00 (±60 min).
- Instill study medication/eye drop after the 08:00 IOP measurement in both eyes. Authorized unmasked study staff should make sure the instillation is performed. Record the morning medication in subject diary.
- Perform IOP measurement at 10:00 (±60 min), and 16:00 (±60 min).
- Perform pupil dilation in both eyes after the 16:00 (±60 min) IOP measurement.
- Perform ophthalmoscopy with pupil dilation in both eyes immediately after the 16:00 IOP measurement.
- Perform GQL-15 questionnaire at any time during this visit.
- An authorized unmasked study staff member, other than the Investigator or Examiner, must:
 - Collect all used and unused bottles of study medication.
 - Collect the paper subject diary.

- If the subject provided written consent to provide a blood sample for a future PGx laboratory research study, the sample must be collected at this visit, if not collected at the previous visits.
- Exit the subject from the study.
- Inform the subjects they will be contacted to confirm AEs by phone call approximately 2 weeks post last study drug administration.

Note:

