12.3.11. Ophthalmoscopy (Fundus) Examination

The ophthalmoscopy (fundus) examination with pupil dilation will be performed for each eye at Visit 1 (Screening), Visit 2 (Baseline, Day 1), and Visit 5 (Month 3) Exit/Early Termination, and graded as described below. The examination will be performed with pupil dilated at Visit 1 (Screening) and Visit 5 (Month 3) Exit. Dilate pupil and ophthalmoscopy examination will be performed after all other ocular procedures have been completed. Cup to disc ratio and abnormality in retina, macula, choroid, and vitreous will also be evaluated.

Glaucomatous Optic Nerve Findings

The optic nerve will be evaluated using a 4-point scale (0-3 scale).

None	(0) =	No damage
Mild	(1) =	Optic nerve damage, secondary to glaucoma including any rim loss (sloping or thinning)
Moderate	(2) =	Optic nerve damage, including cupping to disc margin at one or more points
Severe	(3) =	Optic nerve damage, nearly total cupping, only nasal rim or less present

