10. ANALYSIS OF EXPLORATORY ENDPOINT

Glaucoma Quality of Life-15 (GQL-15) questionnaire (protocol Appendix F) is a 15-item questionnaire measuring the severity of visual disability in glaucoma patients. The GQL-15 will be administered at Baseline (Visit 2, Day 1) and Month 3 (Visit 5).

The GQL-15 total score and 4 domain scores will be summarized descriptively by actual treatment received. In addition, change from baseline will be presented. The 4 domains are central and near vision, outdoor mobility, peripheral vision, and dark adaption and glare.

Table 5 GQL-15 Questionnaire Items Associated with 4 Domains

Domain	Questionnaire Item
Central and near vision	1. Reading newspapers 15. Recognizing faces
Peripheral vision	4. Walking on uneven ground 8. Tripping over objects 9. Seeing objects coming from the side 11. Walking on steps/stairs 12. Bumping into objects 13. Judging distance of foot to step/curb
Glare and dark adaption	2. Walking after dark 3. Seeing at night 5. Adjusting to bright lights 6. Adjusting to dim lights 7. Going from light to dark or vice versa 14. Finding dropped objects
Outdoor mobility	10. Crossing the road

Total score is derived by summing all item-level response scores. Subscale scores are derived by coding the item-level responses on a numerical interval scale ranging from 0 (no difficulty) to 100 (severe difficulty). Subscale scores are average of the sum of scores generated for the item-level subscale responses. Higher subscale scores indicate lower QOL and greater difficulty with subscale specific tasks (Nelson et al, 2003; Sencanic et al, 2018).

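### The GQL-15 must come before the scheduled pupil dilation at baseline but may follow it at Month 3, which could affect the descriptive within-arm change from baseline

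*Protocol*

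**What the plan says.** The GQL-15 is given twice, at Baseline and at Month 3. The timing rules differ.

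- **Visit 2 (Protocol Section 8.1.3):** "Perform GQL-15 questionnaire at any time during this visit prior to 16:00 IOP measurement". Dilation and ophthalmoscopy follow the 16:00 reading.
- **Visit 5 (Protocol Section 8.1.6):** "Perform GQL-15 questionnaire at any time during this visit", with no latest time. The bullet comes after "Perform pupil dilation in both eyes after the 16:00" and after "Perform ophthalmoscopy with pupil dilation in both eyes immediately after the 16:00 IOP measurement".

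The other places that could settle the order do not. Footnote p of the schedule (Protocol Table 3, repeated in SAP Table 1) says only "GQL-15 questionnaire will be administered by subject". Protocol Section 12.3.11 says "Dilate pupil and ophthalmoscopy examination will be performed after all other ocular procedures have been completed", which does not name the questionnaire.

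The objective in Protocol Section 3.4 is exploratory: "To explore Quality of Life in subjects with POAG or OHT". Protocol Section 9.9 plans descriptive summaries of the total and domain scores. SAP Section 10 repeats this and says of the same scores, "In addition, change from baseline will be presented".

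**The concern.** The change from baseline subtracts one questionnaire from the other, so the two should be taken under the same conditions. The GQL-15 asks about difficulty with visual tasks. They include reading newspapers, coping with bright light, coping with dim light, and moving between light and dark rooms. Dilated pupils could make these four harder, and a subject filling in the form at that moment might answer accordingly.

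If some subjects did so at Month 3 only, part of any worsening within an arm would come from the order of procedures. The trial has no untreated arm that would show such a shift separately. I found no instruction in either document to record whether the form was completed before or after dilation, so the effect could not readily be examined afterwards.

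**Working it through.** The plan states no figure on this point, so there is none to reproduce. The check is a comparison of the texts, followed by an illustration of size.

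**1. Is completion after dilation possible?**

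| | Visit 2 | Visit 5 |
|---|---|---|
| Latest time for GQL-15 | before the 16:00 IOP reading | none stated |
| Dilation | after the 16:00 IOP reading | after the 16:00 IOP reading |
| Place of GQL-15 in the list | before dilation | after dilation and ophthalmoscopy |
| Form after the 16:00 dilation? | excluded | permitted |

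The rule in Section 12.3.11 concerns ocular procedures. A self-completed questionnaire is not clearly one of these, and the specific Visit 5 instruction allows any time. The gap stays open.

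**2. How large could the shift be?**

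From the documents:
- Each item is scored 1 to 5 for difficulty (Protocol Appendix F), and the total is the sum over items (SAP Section 10).
- Domain scores are averages of items recoded to 0-100 (SAP Section 10). Five categories at equal spacing give 100 / 4 = 25 points per category.
- The glare and dark-adaption domain has six items (SAP Table 5 of Section 10). Three of the four items named above belong to it; reading newspapers belongs to central and near vision.

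Assumed, with no source in the documents:
- p, the share completing the form after dilation at Month 3: 10%, 30% or 60%.
- Those subjects score one category worse on the four named items and the same on the rest.

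Formulas:
- Shift in mean total = p x 4 x 1.
- Shift in mean glare and dark-adaption score = p x 25 x 3/6 = p x 12.5.

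| p | Total score | Glare and dark-adaption (0-100) |
|---|---|---|
| 10% | 0.10 x 4 = 0.4 | 0.10 x 12.5 = 1.25 |
| 30% | 0.30 x 4 = 1.2 | 0.30 x 12.5 = 3.75 |
| 60% | 0.60 x 4 = 2.4 | 0.60 x 12.5 = 7.5 |

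If nobody completes the form after dilation, p = 0 and both shifts are 0.

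**3. What happens between arms?**

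Bias in the difference = (p in DE-126 arm - p in timolol arm) x shift per affected subject. Both arms follow the same Visit 5 text under masked 1:1 randomization, so the two shares are equal in expectation and the bias is 0. It is non-zero only if timing differs by arm. For example, 60% against 40% with a 4-point shift gives 0.20 x 4 = 0.8 points on the total. Nothing in the documents suggests such a difference.

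**The case against.** The strongest reply is that the text permits completion after dilation but does not direct it. The visit runs from 08:00 to 16:00 with hours between readings, dilation comes only after the last reading, and an instruction to do something at any time overrides the order of the list. No passage says that any subject will fill in the form dilated. The questionnaire also asks about daily activities in general and does not tell subjects to rate their vision at that moment. All of this stands, and it is why the point says that the change could be affected.

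A second reply is that the Visit 2 limit may serve another purpose. Randomization and dispensing follow the 16:00 reading, so the limit also keeps the baseline form ahead of allocation, a reason that does not apply at Visit 5. The documents do not state the purpose, so the difference is not proof of an oversight. It still leaves the two assessments open to different pupil conditions.

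A reader might go further and infer any of the following. The documents do not support them.

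- **That the change from baseline is biased.** This needs completion after dilation and an effect on the answers; neither is established.
- **That the quality-of-life objective rests on this change.** The objective is exploratory, Protocol Section 9.9 does not mention change, and SAP Section 10 adds it as a further descriptive display.
- **That the treatment comparison is distorted.** The same rule applies to both arms. Variation in habit between sites adds noise, but not a bias between arms.
- **That every glare and dark-adaption item would worsen.** The argument from dilation covers three of the six, plus reading. Shifting all six without a stated reason would overstate the size.

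One limit applies to the baseline side. Footnote m allows screening ophthalmoscopy at any time, so where Visits 1 and 2 are combined, the Visit 2 rule guarantees only that the form precedes the scheduled 16:00 dilation.

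**Conclusion.** The point holds as a minor one. The timing rules differ, no other section closes the gap, and Month 3 questionnaires may be completed with dilated pupils while baseline ones must precede that visit's 16:00 dilation. What could be affected is the within-arm descriptive change from baseline in an exploratory outcome.

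The size is unknown. The illustrated shifts rest wholly on an assumed share of 10% to 60% and an assumed one-category worsening on four items. Confidence is high for the difference in wording and low for any effect on the scores. Type I error, power and sample size are untouched.

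**What to change.** In Protocol Section 8.1.6, replace the Visit 5 instruction with the one already used at Visit 2, "Perform GQL-15 questionnaire at any time during this visit prior to 16:00 IOP measurement", and move the bullet above the two dilation bullets. Add the same timing for both visits to footnote p in Protocol Table 3 and SAP Table 1. If the limit is followed, p = 0 and this source of difference at the scheduled 16:00 dilation is removed.

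The cost is one line of wording in Section 8.1.6 and one footnote in each document. No procedure or visit time is added.

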8.1.7. Follow-up (2 Weeks +7 days Post Last Study Drug Administration)

- After 2 weeks post last study drug administration, a follow-up phone call visit will be conducted.

8.2. Study Termination

Santen may stop this study at any time by appropriate notification.

8.3. Efficacy Parameter

The IOP (mmHg) measured in the study eye (identified by the IOP values at baseline visit) is the efficacy measure for this study. The IOP at each scheduled time point (08:00, 10:00, and 16:00) will be evaluated at each post-baseline visit. Besides observed IOP measurements, change and percent change from baseline in IOP at each scheduled time point as well as the change and percent change from baseline in mean diurnal IOP will also be derived and evaluated.

8.4. Safety Parameters

In addition to observed values, changes from baseline will be evaluated at relevant post baseline visits. For a safety outcome measure, the baseline value will be the last observation of that outcome measure prior to the first dose of study medication.

8.4.1. Ocular Assessments

Ocular assessments include:

- BCVA
- Slit-lamp biomicroscopy findings: anterior chamber cells, anterior chamber flare, lid hyperemia, lid edema, conjunctival hyperemia, conjunctival chemosis, corneal edema, corneal staining, keratic precipitate, lens, anterior synechiae of iris, posterior synechiae of iris, iris color abnormalities, eyelash abnormalities, and eyelid abnormalities

- Ophthalmoscopy variables: glaucomatous optic nerve

8.4.2. Non-ocular Assessments

Non-Ocular assessments include:

- Vital Signs (blood pressure and pulse rate)

8.5. Other Assessments

8.5.1. Demographic and Other Assessments

Subject demographics, medical history, concomitant medications, and exposure to study medication will be summarized.

8.5.2. Pharmacogenomics/Genomics

For future exploratory research, blood sample will be collected from the participants who have consented to participate in the collection.

8.5.3. Glaucoma Quality of Life (GQL-15) Questionnaire

The GQL-15 ([Section 12.6](#), Appendix F) is a 15-item questionnaire assessing the quality of life in glaucoma patients by measuring the severity of visual disability. The GQL-15 will be completed by the subject at Baseline (Visit 2, Day 1) and Month 3 (Visit 5). The GQL-15 questionnaire will be used as an exploratory outcome in this study.

8.6. Assessment of Safety

8.6.1. Adverse Events and Serious Adverse Events

8.6.1.1. Definition of Adverse Events

An AE is any untoward medical occurrence in a patient or clinical study participant, temporally associated with the use of study intervention, whether or not considered related to the study intervention. An AE does not necessarily have a causal relationship with the study medication. For this study, the investigational products are DE-126, DE-126 vehicle, and Timolol.

Regardless of relationship to the study medication, an AE can be a clinically relevant unintended sign (including an abnormal laboratory finding), symptom, or disease.

Any significant change in a subject's condition from the time that written informed consent is obtained, regardless of causality, is to be considered an AE. A clinically significant worsening in severity, intensity, or frequency of a pre-existing condition may indicate an AE.

An elective surgical procedure scheduled or planned prior to study entry that does not require overnight hospitalization is not considered an AE, and the underlying diagnosis for the procedure should be captured in the medical history as a pre-existing condition. The surgical procedure should also include the term "elective" in all reports. An elective or planned hospitalization must be reported as an SAE.

The lack of efficacy of the study medication for the condition being investigated is not considered an AE unless a clinically significant change is assessed by the Investigator.

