8.6.1.2. Assessment of Adverse Events

Investigators will seek information on AEs at each subject contact. Subjects should be asked using a general, non-direct question if there has been any change in their general health. Direct questioning and examination should then be performed as appropriate.

Severity of the AE should be assessed according to the following criteria:

Mild: No interference with the subject's daily activities; no medical intervention/therapy required.

Moderate: Possible interference with the subject's daily activities; no or minimal medical intervention/therapy required.

Severe: Considerable interference with the subject's daily activities; medical intervention/therapy required.

Regardless of severity, some events may also meet regulatory serious criteria. Refer to definitions and reporting of serious adverse events (SAEs) in [Section 12.4](#), Appendix D.

An Investigator who is medically qualified must make the determination of relationship (related or not related) to the investigational product for each AE or SAE. When determining relationship to study medication, the Investigator will consider any investigational products that a subject could be exposed to in this clinical trial. The Investigator should decide whether there is a reasonable possibility that the study medication caused the event, taking into account the following: a) evidence, b) science-based rationale, c) medical and clinical judgment, d) mechanisms of action, e) biologic plausibility, f) confounding risk factors (i.e., medical history, concomitant medications), g) temporal relationship, h) dechallenge/rechallenge, and i) lack of alternative explanation.

- The event may be recorded as Related to investigational product or
- Reporting the event as Not Related to study medication be considered

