8.6.2. Serious Adverse Events

8.6.2.1. Assessment of Serious Adverse Events

An AE is considered serious if it fulfills one or more of the following criteria:

- Death (i.e., the AE caused or led to death).

- It was life threatening (i.e., immediately life-threatening).
- It required or prolonged inpatient hospitalization.
- It resulted in a persistent or significant disability/incapacity (i.e., the AE resulted in a substantial disruption of the subject's ability to carry out normal life functions).
- It resulted in a congenital anomaly/birth defect in the offspring of a study subject who was exposed to study therapy prior to conception or during pregnancy.
- It is a medically significant event(s), which may include "sight-threatening events" that may not meet any of the above serious criteria but may jeopardize the subject or require medical or surgical intervention to prevent one of the outcomes listed above.
 - Sight threatening event: A sight-threatening event is any event that places the subject at immediate risk of permanently losing vision in either eye as a direct result of the event.

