
 • Any abnormal laboratory test results (hematology, clinical chemistry, or urinalysis) or other safety assessments (e.g., ECG, radiological scans, vital signs measurements), including those that worsen from baseline, considered clinically significant in the medical and scientific judgment of the investigator (and not related to progression of underlying disease, unless judged by the investigator to be more severe than expected for the subject's condition). • Exacerbation of a chronic or intermittent pre-existing condition including either an increase in frequency and/or intensity of the condition. • New conditions detected or diagnosed after study intervention administration even though it may have been present before the start of the study. • Signs, symptoms, or the clinical sequelae of a suspected drug-drug interaction. • Signs, symptoms, or the clinical sequelae of a suspected overdose of either study intervention or a concomitant medication. Overdose per se will not be reported as an AE/SAE unless it is an intentional overdose taken with possible suicidal/self-harming intent. Such overdoses should be reported regardless of sequelae. • “Lack of efficacy” or “failure of expected pharmacological action” per se will not be reported as an AE or SAE. Such instances will be captured in the efficacy assessments. However, the signs, symptoms, and/or clinical sequelae resulting from lack of efficacy will be reported as AE or SAE if they fulfil the definition of an AE or SAE.
Events NOT Meeting the AE Definition

 • Any clinically significant abnormal laboratory findings or other abnormal safety assessments which are associated with the underlying disease, unless judged by the investigator to be more severe than expected for the participant's condition. • The disease/disorder being studied or expected progression, signs, or symptoms of the disease/disorder being studied, unless more severe than expected for the participant's condition. • Medical or surgical procedure (e.g., endoscopy, appendectomy): the condition that leads to the procedure is the AE. • Situations in which an untoward medical occurrence did not occur (social and/or convenience admission to a hospital). • Anticipated day-to-day fluctuations of pre-existing disease(s) or condition(s) present or detected at the start of the study that do not worsen.

2. Definition of SAE

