A SAE is defined as any untoward medical occurrence that, at any dose:

 a. Results in death

 b. Is life-threatening

The term 'life-threatening' in the definition of 'serious' refers to an event in which the participant was at risk of death at the time of the event. It does not refer to an event, which hypothetically might have caused death if it were more severe.

 c. Requires inpatient hospitalization or prolongation of existing hospitalization 
In general, hospitalization signifies that the participant has been detained (usually involving at least an overnight stay) at the hospital or emergency ward for observation and/or treatment that would not have been appropriate in the physician's office or outpatient setting. Complications that occur during hospitalization are AEs. If a complication prolongs hospitalization or fulfills any other serious criteria, the event is serious. When in doubt as to whether "hospitalization" occurred or was necessary, the AE should be considered serious.
 
Hospitalization for elective treatment of a pre-existing condition that did not worsen from baseline is not considered an AE.

 d. Results in persistent disability/incapacity 
 • The term disability means a substantial disruption of a person's ability to conduct normal life functions. • This definition is not intended to include experiences of relatively minor medical significance such as uncomplicated headache, nausea, vomiting, diarrhea, influenza, and accidental trauma (e.g., sprained ankle) which may interfere with or prevent everyday life functions but do not constitute a substantial disruption.

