4.3.1.1. Serious Adverse Event

An AE will be counted as a *serious adverse event* (SAE) if the Clinical Investigator selected “Yes” under Item 5 (Is the adverse event serious?) on the AE eCRF. Any AE is considered a SAE if it fulfills one or more of the following criteria:

- Death (i.e., the AE caused or led to death)
- Life threatening (i.e., immediately life-threatening)
- Inpatient hospitalization and/or prolonged hospitalization

- A persistent or significant disability/incapacity (i.e., the AE resulted in a substantial disruption of the subject's ability to carry out normal life functions)
- A congenital anomaly/birth defect in the offspring of a study subject who was exposed to study therapy prior to conception or during pregnancy
- Sight threatening event
- Other medically important event (e.g. requires medical or surgical intervention to prevent one or more of the listed above)

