9.1. Adverse Event

Subjects with any AEs will be tabulated AEs by treatment arm using actual treatment received. Subjects with any AEs will be tabulated by SOC and PT where a subject who experienced multiple AEs within a SOC or PT will be counted only once for that SOC or PT. SAEs, SARs, and Serious SARs will be tabulated similarly.

Subjects with any ocular and non-ocular AEs will be tabulated separately. AEs, ocular, and non-ocular will also be summarized by relationship to treatment and maximum severity. Any ocular AE that occurred simultaneously to both eyes will be counted once.

AE, SARs, ocular and non-ocular AEs will also be summarized by country.

AEs, AEs leading to death, AEs leading to discontinuation, SAEs, and ESIs, if any, will be listed separately.

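### For elective hospitalisation of a pre-existing condition that did not worsen, the protocol requires an SAE report in one section and says it is not an AE in another

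*Protocol*

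**What the plan says.** Protocol 8.6.1.1 exempts only one kind of elective event. A surgical procedure planned before study entry "that does not require overnight hospitalization is not considered an AE". The paragraph then closes with an unqualified rule: "An elective or planned hospitalization must be reported as an SAE".

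Appendix D (12.4), Definition of SAE, item c, discusses hospitalisation as a seriousness criterion and ends: "Hospitalization for elective treatment of a pre-existing condition that did not worsen from baseline is not considered an AE". Its list of events that do not meet the AE definition also includes "Situations in which an untoward medical occurrence did not occur (social and/or convenience admission to a hospital").

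Protocol 8.6.1.2 sends sites to Appendix D: "Refer to definitions and reporting of serious adverse events (SAEs) in" that appendix. It gives no order of precedence.

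The other definitions carry no elective exception. Protocol 8.6.2.1 lists "It required or prolonged inpatient hospitalization"; SAP 4.3.1.1 lists "Inpatient hospitalization and/or prolonged hospitalization". Under SAP 4.3.1.1 an event is an SAE when the investigator answers yes to the seriousness item on the AE form. SAP 9.1 then tabulates AEs by system organ class and preferred term, and adds: "SAEs, SARs, and Serious SARs will be tabulated similarly".

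**The concern.** A site that relies on 8.6.1.1 must report a planned overnight admission as an SAE within 24 hours (8.6.2.2 and 8.6.5). A site that follows the reference to Appendix D would, where the condition is stable, report nothing as an AE. Both sites would be following current protocol text, and each would breach the other section.

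Two things are at stake. One is compliance with a mandatory expedited reporting rule. The other is consistency of the SAE and AE tables across about 45 sites, because the analysis takes the site's classification as given.

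**Working it through.** The plan gives no figure on this point, so the check is a comparison of texts followed by one line of arithmetic.

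**Step 1. Take a test case.** During treatment, a subject is admitted overnight for a pre-planned procedure for a condition that was present at baseline and has not worsened.

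| Text | Result |
|---|---|
| Protocol 8.6.1.1, exemption | Does not apply, because there is an overnight stay |
| Protocol 8.6.1.1, closing sentence | 1 SAE |
| Appendix D, SAE item c | 0 AEs, and therefore 0 SAEs |
| Protocol 8.6.2.1 | Hospitalisation makes an AE serious; does not say whether this is an AE |
| SAP 4.3.1.1 | Follows the investigator's entry |

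No reading satisfies the second and third rows together, since an event that is not an AE cannot be an SAE.

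**Step 2. Find where the conflict stops.** Item c applies only to elective treatment of a pre-existing condition that did not worsen. For a new or worsened condition that exclusion is silent, so it does not contradict 8.6.1.1. A planned social or convenience admission is a smaller second overlap, through the Appendix D list of events that are not AEs.

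**Step 3. Look for a tie-breaker.**
- Sections 8.6.1.2 and 8.6.5 refer to Appendix D, but neither says that it overrides the body.
- Appendix D says that doubt about whether hospitalisation occurred or was necessary is resolved toward serious. That presupposes an AE, which item c denies here.
- Section 8.6.2.2 tells sites to record the illness behind a surgical or diagnostic hospitalisation as the SAE, again without an elective exception.
- The Amendment 1 summary lists no change to 8.6.1.1 or Appendix D, so both sentences stand as current text.

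**Step 4. Size of one discordant case.** With the planned numbers, one subject is 1/147 = 0.68 percentage points of an arm and 1/294 = 0.34 points overall. Only treatment-emergent events are tabulated (SAP 4.3.1), so an admission before first dose affects reporting but not the tables. The documents give no expected number of elective admissions, so a total cannot be computed.

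**The case against.** The strongest reply is that the practical effect is small. It has five parts.

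- **Scope.** The sections do not conflict for elective admissions in general, only for stable pre-existing conditions. Ocular surgery is prohibited throughout the study (exclusion 10 and 6.3.1), and treatment lasts three months, so some likely admissions are already ruled out. This stands, and the point is limited accordingly.
- **Traceability.** A reader might infer that an admission handled under Appendix D leaves no record. The documents do not support that. Section 12.3.2 requires surgical procedures during the study to be entered in source documents with indication and dates, and 6.3 requires concomitant treatment in source and on the eCRF. What is lost is the AE or SAE report.
- **Visibility.** Section 8.6.1.1 asks that elective procedures be labelled as such in reports, and SAP 9.1 lists SAEs separately. Elective admissions that were reported can therefore be picked out. Those that were not reported cannot be found in those listings.
- **Bias.** Allocation is randomised and investigators are masked (Protocol 6.5), and SAP 6 plans no statistical testing of safety measures. Randomisation is not stratified by site, so chance imbalance is possible, but nothing ties a site's reading to treatment arm.
- **Magnitude.** The preceding Phase IIb study is described in Protocol 2.2 as having one SAE. A reader might infer that a few admissions would multiply the SAE count in this trial. The documents give neither that study's size nor its rule for elective admissions, and no forecast for this one, so the inference has no support.

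These replies narrow the consequence. None of them reconciles the two sentences.

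**Conclusion.** The protocol contradicts itself on a mandatory reporting rule. For an elective or planned overnight hospitalisation for a pre-existing condition that did not worsen from baseline, 8.6.1.1 requires an SAE report and Appendix D says there is no AE. The SAP passes the site's choice into the tables. Each such admission during treatment counts as one SAE or none; how many there will be is unknown.

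The effect is limited to SAE reporting and to descriptive tables of treatment-emergent events. The primary and key secondary analyses, the type I error rate and the sample size are not affected, and a systematic difference between arms is not shown. The conclusion rests on the wording alone and assumes no event rate. It does not say which of the two rules is right.

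**What to change.** Reconcile the two passages into one rule, stated once in Appendix D, and replace the closing sentence of the elective-procedure paragraph in 8.6.1.1 with a cross-reference to it. Make the rule cover planned social or convenience admissions as well. Align Protocol 8.6.2.1, Protocol 8.6.2.2 and SAP 4.3.1.1 with it; otherwise the inconsistency would survive in the sections that mention hospitalisation without an elective exception.

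Before database lock and unmasking, apply the rule to every hospitalisation. A review of reported events alone would miss admissions that sites left out under Appendix D. It should therefore also draw on the procedure and concomitant-therapy records and on the source data verification already planned in Protocol 10.1.

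The cost is a protocol and SAP clarification and a short masked review. No new data collection is needed beyond site queries.
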